10.11.11.2. Analysis Sets

For purposes of analysis, the following analysis sets are defined in Substudy A:

Population	Description
Enrolled	All participants who sign the ICD.
Randomized population	All participants who are assigned a randomization number in the IWR system regardless of whether the study intervention was administered.
Safety population	All participants who receive the study intervention.
mitT immunogenicity population	All randomized participants who receive the study intervention and have at least 1 valid and determinate assay result after vaccination.
Evaluable immunogenicity population	All participants who are eligible, receive the study intervention to which they were randomized, have the 1-month postvaccination blood collection within an appropriate window, have no major protocol violations from randomization through the 1-month postvaccination blood draw, and have at least 1 valid and determinate assay result at the 1-month postvaccination visit.

10.11.11.3. Statistical Analyses

10.11.11.3.1. General Considerations

Refer to [Section 9](#) for general considerations of statistical analyses.

10.11.11.3.2. Primary Endpoint(s)/Estimand(s) Analysis

Endpoint	Statistical Analysis Methods
Safety	
 Descriptive statistics will be provided for each reactogenicity endpoint in each vaccine group (Group 1 to Group 7 individually). Local reactions (pain at the injection site, redness, and swelling) and systemic events (fever, fatigue, headache, chills, vomiting, diarrhea, new or worsened muscle pain, and new or worsened joint pain) from Day 1 through Day 7 after vaccination will be presented by maximum severity and any severity. Descriptive summary statistics will include counts and percentages of participants with the indicated endpoint and the associated Clopper-Pearson 95% CIs (Section 9.3.1). AEs and SAEs will be categorized according to MedDRA terms. All of the AEs reported through the 1-month follow-up visit and SAEs reported throughout the study will be descriptively summarized with counts, percentages, and associated Clopper-Pearson 95% CI for each vaccine group (Section 9.3.1).
Immunogenicity	
 GMRs of RSV A and RSV B NTs (Group 1 to Group 4), GMRs of SARS-CoV-2 Omicron BA.4/BA.5–strain NTs and reference-strain NTs (Group 1 to Group 3), influenza strain-specific GMRs of HAI titers (Group 1 to Group 5) at 1 month after vaccination will be provided with 97.5% CIs (Section 9.3.1.2.3). Using a 2-fold noninferiority margin, success for the first primary immunogenicity objective will be declared if the lower bound of the 2-sided 97.5% CI for the GMR is greater than 0.5 for both RSV A and RSV B antigens, for both the Omicron BA.4/BA.5 and reference strains, and for all 4 QIV strains. GMRs of RSV A and RSV B NTs (Group 2 to Group 4) and GMRs of SARS-CoV-2 Omicron BA.4/BA.5–strain NTs and reference-strain NTs (Group 2 to Group 3) at 1 month after vaccination will be provided with 97.5% CIs (Section 9.3.1.2.3). Using a 2-fold noninferiority margin, success for the second primary immunogenicity objective will be declared if the lower bound of the 2-sided 97.5% CI for the GMR is greater than 0.5 for both RSV A and RSV B antigens and for both the Omicron BA.4/BA.5 and reference strains.

10.11.11.3.3. Secondary Endpoint(s)/Estimand(s) Analysis

Endpoint	Statistical Analysis Methods
Secondary immunogenicity	
 • GMRs of RSV A and RSV B NTs (Group 7 to Group 4), GMRs of SARS-CoV-2 Omicron BA.4/BA.5–strain NTs and reference-strain NTs (Group 7 to Group 3), influenza strain-specific GMRs of HAI titers (Group 7 to Group 5) at 1 month after vaccination will be provided with 97.5% CIs (Section 9.3.1.2.3). Using a 2-fold noninferiority margin, success for the first of the secondary immunogenicity objectives will be declared if the lower bound of the 2-sided 97.5% CI for the GMR is greater than 0.5 for both RSV A and RSV B antigens, for both the Omicron BA.4/BA.5 and reference strains, and for all 4 QIV strains, after the first primary immunogenicity objective is achieved. • GMRs of RSV A and RSV B NTs (Group 6 to Group 4) and GMRs of SARS-CoV-2 Omicron BA.4/BA.5–strain NTs and reference-strain NTs (Group 6 to Group 3) at 1 month after vaccination will be provided with 97.5% CIs (Section 9.3.1.2.3). Using a 2-fold noninferiority margin, success for the second of the secondary immunogenicity objectives will be declared if the lower bound of the 2-sided 97.5% CI for the GMR is greater than 0.5 for both RSV A and RSV B antigens and for both the Omicron BA.4/BA.5 and reference strains, after the second primary immunogenicity objective is achieved.

10.11.11.3.4. Exploratory Endpoint(s) Analysis

Endpoint	Statistical Analysis Methods
Exploratory	
 • GMTs of NTs for each RSV subgroup (A or B), GMTs of QIV strain-specific HAI titers, and GMTs of SARS-CoV-2 strain-specific NTs will be descriptively summarized with 2-sided 95% CIs for each applicable vaccine group both before vaccination and at the 1-month postvaccination visit (Section 9.3.1). • GMFRs of NTs for each RSV subgroup (A or B), GMFRs of influenza strain-specific HAI titers, and GMFRs of SARS-CoV-2 strain-specific NTs from before vaccination to the 1-month postvaccination visit will be descriptively summarized with 2-sided 95% CIs for each applicable vaccine group (Section 9.3.1).

Endpoint	Statistical Analysis Methods
	
 The number and percentage of participants achieving strain-specific HAI seroconversion, SARS-CoV-2 strain-specific seroresponse at 1 month after vaccination, and the number and percentage of participants with strain-specific HAI titers $\geq 1:40$ before vaccination and 1 month after vaccination will be summarized with 2-sided Clopper-Pearson 95% CIs for each applicable vaccine group (Section 9.3.1). 
Note: HAI seroconversion is defined as an HAI titer $< 1:10$ prior to vaccination and $\geq 1:40$ at the postvaccination visit, or an HAI titer of $\geq 1:10$ prior to vaccination with a 4-fold rise at the postvaccination visit. SARS-CoV-2 seroresponse is defined as achieving a ≥ 4-fold rise from baseline (before the study vaccination). If the baseline measurement is below the LLOQ, the postvaccination measure of $\geq 4 \times \text{LLOQ}$ is considered seroresponse.
 
 GMTs may be compared between other vaccine groups (eg, Group 1 vs Group 2; Group 1 vs Group 7; Group 2 vs Group 6; etc) with GMRs and associated 2-sided 95% CIs (Section 9.3.1.2.3).

10.11.11.4. Interim Analyses

No formal interim analysis will be conducted for this study phase.

The primary analysis will be performed on safety and immunogenicity data through 1 month after vaccination (ie, Visit A102); all type I error will be spent at this analysis. Once this analysis has been completed, study participants and the study team may be unblinded to study intervention allocation.

6-Month safety data will be summarized when they become available.

10.11.11.5. Sample Size Determination

[Table 5](#) presents the power to demonstrate the noninferiority for each antigen included in Group 1 ([RSVpreF+BNT162b2] + QIV) as well as the power to demonstrate the noninferiority for each antigen included in Group 2 ([RSVpreF+BNT162b2] + placebo). The power for the secondary objectives is similar to that for the primary objectives as the comparisons and assumptions are similar.

For all assay results, no interference is assumed (ie, GMR=1). The SDs of the log titers are based on different reference studies. With 135 evaluable participants per vaccine group, there is ~90% power to declare noninferiority for all 8 antigens included in Group 1, and ~92% power to declare noninferiority for all 4 antigens included in Group 2. Power was calculated with PROC POWER in SAS using the TWOSAMPLEMEANS statement. Assuming 10% of the participants are nonevaluable, approximately 150 participants per group need to be enrolled for Groups 1 through 7.

Table 5. Power to Demonstrate Noninferiority (N=135 per Group)

Vaccine Component (SD Reference Study)	Antigen/Endpoint	Common SD (Log e Scale)	Difference (Log e Scale)	Noninferiority Margin	Power to Declare Noninferiority (1-Sided Alpha = 0.0125)
RSVpreF (C3671013)	RSV A NT	1.1	0	2-Fold	99.8%
	RSV B NT	1.1	0	2-Fold	99.8%
BNT162b2 (C4591044)	SARS-CoV-2 Omicron BA.4/BA.5–strain NTs	1.5	0	2-Fold	93.8%
	SARS-CoV-2 reference-strain NTs	1.3	0	2-Fold	98.3%
QIV (C3671006)	H1N1 HAI	1.1	0	2-Fold	99.8%
	H3N2 HAI	1.1	0	2-Fold	99.8%
	B strain 1 HAI	1.2	0	2-Fold	99.3%
	B strain 2 HAI	1.2	0	2-Fold	99.3%
Overall power to reject all 8 tests (Group 1 or 7 vs Group 4, Group 1 or 7 vs Group 3, Group 1 or 7 vs Group 5)					90.2%
Overall power to reject all first 4 tests (Group 2 or 6 vs Group 4, Group 2 or 6 vs Group 3)					91.8%

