10.11.11.1.5. Multiplicity Adjustment

Type I error of 5% is equally split between the 2 primary immunogenicity objectives (2-sided 2.5% for each). The first primary immunogenicity objective will be achieved if all 8 null hypotheses are rejected. The second primary immunogenicity objective will be achieved if all 4 null hypotheses are rejected. The study is considered successful if either primary immunogenicity objective is achieved.

The secondary immunogenicity objectives will be tested sequentially after the primary objective(s) is achieved as described in the schema below.

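### Table 5 gives the secondary objectives the primary objectives' power (90.2% and 91.8%); once the sequential gate is counted, it is about 83% and 86% on the protocol's own assumptions

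*Protocol*

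**What the plan says.** Protocol section 10.11.11.5 sizes the trial at 135 evaluable participants per group. It claims for the first primary objective: "With 135 evaluable participants per vaccine group, there is ~90% power to declare noninferiority for all 8 antigens included in Group 1". The assumption on effect is: "For all assay results, no interference is assumed (ie, GMR=1". On the secondary objectives it says: "The power for the secondary objectives is similar to that for the primary objectives as the comparisons and assumptions are similar".

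Table 5 carries this through. Its first summary row begins "Overall power to reject all 8 tests (Group 1 or 7 vs Group 4" and gives 90.2%. The second summary row covers Groups 2 and 6 in the same way and gives 91.8%.

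The success rule is elsewhere. Section 10.11.11.1.5 (Multiplicity Adjustment) says: "The secondary immunogenicity objectives will be tested sequentially after the primary objective(s) is achieved". SAP section 5.1.5 repeats this. Section 10.11.11.3.3 makes it specific: the Group 7 objective needs every lower 97.5% confidence bound above 0.5, and success counts only "after the first primary immunogenicity objective is achieved". The Group 6 objective is tied to the second primary objective in the same way.

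**The concern.** The event that Table 5 evaluates for Groups 7 and 6 is not the event that the protocol defines as success. Table 5 gives the chance that the secondary tests pass on their own. The protocol requires the primary tests to pass as well. A joint event cannot be more probable than either part, so the printed figures are upper limits, reached only if secondary success never occurs without primary success.

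Groups 6 and 7 account for 300 of the 1050 participants and carry formal noninferiority objectives. A reader judging whether these arms are adequately powered is given a figure that is too high, and nothing in the sample size section mentions the gate.

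**Working it through.** **Inputs (Protocol section 10.11.11.5 and Table 5 unless noted)**
- n = 135 evaluable per group, so df = 2 × 135 − 2 = 268.
- Margin 2-fold: ln 2 = 0.693. True log difference 0.
- Level: "Power to Declare Noninferiority (1-Sided Alpha = 0.0125" per test, consistent with section 10.11.11.1.5: "Type I error of 5% is equally split between the 2 primary immunogenicity objectives (2-sided 2.5% for each".
- SDs on the natural-log scale: RSV A and RSV B 1.1; BA.4/BA.5 1.5; SARS-CoV-2 reference strain 1.3; H1N1 and H3N2 1.1; both B strains 1.2.
- Comparators: Groups 4, 3 and 5 serve both the primary and the secondary tests (sections 10.11.11.1.1 to 10.11.11.1.4).

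**Step 1. Reproduce the plan's figures.** The noncentrality is 0.693 / (SD × √(2/135)) and the critical t is 2.254. Noncentral-t power per antigen:

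| SD | Noncentrality | Power | Table 5 |
|---|---|---|---|
| 1.1 | 5.177 | 99.8% | 99.8% |
| 1.2 | 4.746 | 99.35% | 99.3% |
| 1.3 | 4.381 | 98.3% | 98.3% |
| 1.5 | 3.797 | 93.8% | 93.8% |

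Multiplying across antigens gives 90.3% (8 tests) and 91.9% (4 tests). Multiplying Table 5's rounded entries gives 90.2% and 91.8%. Table 5 therefore treats antigens as independent and includes no gate.

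**Step 2. Correlation between a primary test and its secondary counterpart.** For one antigen the two differences are, for example, Group 1 − Group 4 and Group 7 − Group 4. Each has variance 2σ²/n and they share the Group 4 term, with covariance σ²/n. The correlation is 1/2.

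**Step 3. Probability that both tests pass, per antigen.** From a bivariate normal with correlation 0.5 and the t critical value:

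| SD | Both pass |
|---|---|
| 1.1 | 0.9966 |
| 1.2 | 0.9880 |
| 1.3 | 0.9692 |
| 1.5 | 0.8933 |

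**Step 4. Gated power, independent antigens.**
- Group 1 then Group 7: 0.9966⁴ × 0.8933 × 0.9692 × 0.9880² = 0.834.
- Group 2 then Group 6: 0.9966² × 0.8933 × 0.9692 = 0.860.

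Simulating the t tests with estimated variances (1,000,000 trials) gives 83.2% and 85.8%. The two methods agree to 0.2 points.

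**Step 5. Bounds.** From the stated figures alone, with no assumption about dependence, the joint probability cannot be below 2 × 0.902 − 1 = 80.4% or 2 × 0.918 − 1 = 83.6%. If primary and secondary tests were independent it would be 0.902² = 81.4% and 0.918² = 84.3%. The shared comparators lift it to the Step 4 values.

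**Step 6. Correlation between antigens.** The documents give none, so these values are assumptions:

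| Within / between components | 8-test chain: ungated → gated | 4-test chain: ungated → gated |
|---|---|---|
| 0 / 0 | 90.4% → 83.2% | 91.9% → 85.8% |
| 0.5 / 0 | 91.0% → 84.4% | 92.4% → 86.8% |
| 0.8 / 0 | 91.9% → 86.0% | 93.0% → 88.0% |
| 0.95 / 0.5 | 92.8% → 87.5% | 93.6% → 88.8% |

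No gated value reaches the stated figure, and the gap between ungated and gated stays at about 5 to 7 points.

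**Step 7. Some interference.** At a true GMR of 0.9 for every antigen (an assumption; independent antigens), ungated power is 66.7% and 74.6%, and gated power about 49% and 60%. Most of the fall from the planned figures comes from the changed GMR and affects the primary objectives equally. The part due to the gate grows to about 18 and 14 points.

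**The case against.** The best defence is that the summary rows are labelled as power to reject a set of tests, and for that event 90.2% and 91.8% are correct for Groups 7 and 6 too. Moreover, once the gate has opened, the chance that the secondary objective succeeds is 0.832/0.9037 = 92.1% (8 tests) and 0.858/0.9186 = 93.4% (4 tests), so a conditional reading of similar power would be fair. The gated 83% and 86% also rest on independent antigens, which the documents do not establish. Finally, study success depends on the primary objectives only.

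Part of this stands. The test-level figures are arithmetically right, and the gated figures should carry their assumption. But the sentence in section 10.11.11.5 speaks of power for the objectives, and section 10.11.11.3.3 builds the gate into success on those objectives. The text does not say the power is conditional, and Table 5 is not a conditional calculation. Independence is the assumption that Table 5's own product makes, and relaxing it does not close the gap. The multiplicity schema was not visible in the text reviewed, but section 10.11.11.3.3 states in words both the matching gate and the 97.5% interval, so the result does not depend on the figure.

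**Conclusion.** The concern holds. On the protocol's own assumptions (GMR of 1, Table 5 SDs, 135 per group, independent antigens) and with shared comparators, the power of the gated secondary objectives is about 83% for Group 7 and 86% for Group 6, against the printed 90.2% and 91.8%. The chance of missing the objective is about 17% rather than 9.8%, and about 14% rather than 8.2%. With positive correlation between antigens the gated figures could be about 84–87% and 87–89%.

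This is a misstatement in the planning section. It changes no analysis, decision rule or error rate, and leaves primary power and the sample size as they are. Gated power stays above 80% when GMR is 1.

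**What to change.** In Table 5, restrict 90.2% to Group 1 and 91.8% to Group 2. Add separate entries for Group 7 (about 83%) and Group 6 (about 86%), labelled as joint with the matching primary objective and assuming shared comparators and independent antigens. If the test-level values for Groups 7 and 6 are still wanted, put them in a footnote that says they ignore the gate.

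Replace the sentence on similarity with one such as: *Each secondary objective can succeed only if its matching primary objective is achieved, so its power is lower, about 83% for Group 7 and 86% for Group 6 under the assumptions of Table 5.*

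The cost is two table entries and one sentence in the protocol, and a less favourable stated figure. No change to enrolment, testing or the SAP analyses is needed.

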10.12. Appendix 12: Protocol Amendment History

The protocol amendment summary of changes table for the current amendment is located directly before the TOC. The protocol amendment summary of changes tables for past amendment(s) can be found below:

Description of Change	Brief Rationale	Section # and Name
Substantial Modification(s)		
Added Substudy B	New substudy on alternative formulation of RSVpreF and BNT162b2 (Omi XBB.1.5) combination vaccine [RSVpreF+BNT162b2]	Section 10.12 Appendix 12: Substudy B (Phase 1/2)
Non-substantial Modification(s)		
Updated/removed text in the body of protocol that was specific to Substudy A	Substudy-specific text is included in substudy appendices	Section 1.1 Synopsis Section 2.3.1 Risk Assessment Section 7.2 Participant Discontinuation/Withdrawal From the Study Section 5.4 Screen Failures Section 8.3.1 Physical Examinations Section 8.3.2 Vital Signs Section 8.3.3 Clinical Safety Laboratory Assessments Section 8.4.1 Time Period and Frequency for Collecting AE and SAE Information Section 8.4.8 Adverse Events of Special Interest for Substudy A Section 10.11.4 Introduction – Substudy A
Updated references and text to include Substudy B	Changes to align with master protocol format	Sections 1 through 9 Section 10.1.5.1 Data Monitoring Committee Section 10.2 Appendix 2: Clinical Laboratory Tests Section 10.5 Appendix 5: Genetics

Description of Change	Brief Rationale	Section # and Name
Added stopping rule text for Substudy B	Consistency with Substudy A	Section 1.1 Synopsis
Added IND number and clintrials.gov ID	Not available at the time of original protocol	Title page Section 1.1 Synopsis
Updated text on anaphylaxis and myocarditis assessment for RSVpreF	Consolidated the risk text from RSV and COVID; updated based on the recent updates for both programs	Section 2.3.1 Risk Assessment
Removed text on bivalent BNT162b2 vaccine approval	Updated formulation	Section 2.2.3.1 SARS-CoV-2
Removed collection of date of birth	New requirement	Section 8.1 Administrative Procedures
Added instructions for noting COVID-19 symptoms for Substudy A	Editorial change	Section 10.11.3 SoA – Substudy A
“RSV” was updated to “RSVpreF” as per PACL (26 April 2023)	Correction of typographical error	Section 2.3 Benefit/Risk Assessment
Updated information on RSVpreF	Introductory paragraph on clinical studies	Section 2.2.3.2 RSVpreF Vaccination
Added/updated text Substudy B formulation to read “alternative formulation of RSVpreF and BNT162b2 (Omi XBB.1.5) combination vaccine [RSVpreF+BNT162b2]”	Consistency throughout the document	Section 1: Protocol Summary Section 4.3: Justification for Dose Section 10.12 Appendix 12: Substudy B Section 10.13 Appendix 13: Abbreviations
Added a review of e-diary data from Days 1 through 3 for the first 50 participants in Stratum 1 and the first	Regulatory recommendation since there is no prior human experience with the combined RSVpreF and	Section 10.11.6.1 Overall Design Section 10.11.8.1.4 Allocation to Study Intervention

Description of Change	Brief Rationale	Section # and Name
20 participants in Stratum 2 prior to enrollment of the remaining participants in each group per PACL (01 June 2023)	bivalent BNT162b2 (original/Omi BA.4/BA.5) vaccine	
Stopping rule #2 updated from “troponin I” to “troponin” per PACL (12 July 2023)	To accommodate sites not able to measure troponin I	Section 10.11.10.5 Stopping Rules
“Licensed influenza vaccine” updated to “influenza vaccine” per PACL (12 July 2023)	To accommodate participants that may have received investigational influenza vaccines	Section 10.11.3 SoA – Substudy A (Phase 1/2) Section 10.11.8.7 Prior and Concomitant Therapy Section 10.11.10.7 Study Procedures
Added volume for normal saline placebo per PACL (26 April 2023)	Addition of text that was inadvertently omitted in original protocol	Section 10.11.8 Substudy A Intervention and Concomitant Therapy Section 10.11.8.1 Study Intervention(s) Administered
Added volume for QIV	Addition of text that was inadvertently omitted in original protocol	Section 10.11.8.1 Study Intervention(s) Administered
Updated barrier requirements	New information for Comirnaty and Abrysvo	Section 4.2.3 Choice of Contraception/Barrier Requirements
Removed text inadvertently included previously	Typographical errors corrected	Section 10.11.7.3 Study Procedures Section 10.11.11.2 Analysis Sets Section 10.11.11.3 Statistical Analyses

10.13. Appendix 13: Abbreviations

Abbreviation	Term
ADE	adverse device effect
AE	adverse event
AESI	adverse event of special interest
AKI	acute kidney injury
Al(OH) ₃	aluminum hydroxide
ALT	alanine aminotransferase
ARI-RSV	RSV-associated acute respiratory illness
AST	aspartate aminotransferase
AV	atrioventricular
AxMP	auxiliary medicinal product
BNT162b2	Pfizer's COVID-19 vaccine
CBER	Center for Biologics Evaluation and Research (United States)
CDC	Centers for Disease Control and Prevention (United States)
CFR	Code of Federal Regulations (United States)
ChAdOx1-S	ChAdOx1-S (recombinant) SARS-CoV-2 vaccine (AstraZeneca)
CHF	congestive heart failure
CI	confidence interval
CIOMS	Council for International Organizations of Medical Sciences
CK	creatinine kinase
CKD-EPI	Chronic Kidney Disease Epidemiology Collaboration
CONSORT	Consolidated Standards of Reporting Trials
COPD	chronic obstructive pulmonary disease
COVID-19	coronavirus disease 2019
CpG	CpG 24555
CRF	case report form
CRO	contract research organization
CSR	clinical study report
CT	clinical trial
CTIS	Clinical Trial Information System
DCT	data collection tool
DILI	drug-induced liver injury
DNA	deoxyribonucleic acid
EC	ethics committee
ECC	emergency contact card
ECG	electrocardiogram
eCrCl	estimated creatinine clearance
eCRF	electronic case report form
EDB	exposure during breastfeeding

Abbreviation	Term
e-diary	electronic diary
EDP	exposure during pregnancy
eGFR	estimated glomerular filtration rate
eSAE	electronic safety adverse event
EU	European Union
EUA	emergency use authorization
EudraCT	European Union Drug Regulating Authorities Clinical Trials (European Clinical Trials Database)
FDA	Food and Drug Administration (United States)
FSH	follicle-stimulating hormone
GCP	Good Clinical Practice
GGT	gamma-glutamyl transferase
GMFR	geometric mean fold rise
GMR	geometric mean ratio
GMT	geometric mean titer
HAI	hemagglutination inhibition assay
HBe	hepatitis B e
HBeAg	hepatitis B e antigen
HBsAg	hepatitis B surface antigen
HBV	hepatitis B virus
HCV	hepatitis C virus
HD	high dose
HIV	human immunodeficiency virus
HR	heart rate
HRT	hormone replacement therapy
IB	investigator's brochure
ICD	informed consent document
ICH	International Council for Harmonisation of Technical Requirements for Pharmaceuticals for Human Use
ID	identification
IgG	immunoglobulin G
IMP	investigational medicinal product
IND	investigational new drug
INR	international normalized ratio
IPAL	investigational product accountability log
IPM	investigational product manual
IRB	institutional review board
IRC	internal review committee
IRT	interactive response technology
ISO	International Organization for Standardization

Abbreviation	Term
IV	intravenous(ly)
IWR	interactive Web-based response
KDIGO	Kidney Disease Improving Global Outcomes
LBBB	left bundle branch block
LFT	liver function test
LLOQ	lower limit of quantitation
LNP	lipid nanoparticle
LRTI	lower respiratory tract illness
LRTI-RSV	RSV-associated lower respiratory tract illness
LSLV	last subject last visit
MDR	medical device regulation
MedDRA	Medical Dictionary for Regulatory Activities
mITT	modified intent-to-treat
modRNA	nucleoside-modified messenger ribonucleic acid
MQI	medically qualified individual
mRNA	messenger ribonucleic acid
mRNA-1273	mRNA-1273 SARS-CoV-2 vaccine (Moderna)
NA	not applicable
NAAT	nucleic acid amplification test
N-binding	SARS-CoV-2 nucleoprotein-binding
NIMP	noninvestigational medicinal product
NT	neutralizing titer
Omi	Omicron
PACL	protocol administrative change letter
PFS	prefilled syringe(s)
PI	principal investigator
PSSA	Pfizer's Serious Adverse Event Submission Assistant
PT	prothrombin time
PVC	premature ventricular contraction
QIV	quadrivalent influenza vaccine
QTcF	QT interval corrected by the Fridericia formula
QTL	quality tolerance limit
RCDC	reverse cumulative distribution curve
RNA	ribonucleic acid
RSV	respiratory syncytial virus
RSV A	respiratory syncytial virus subgroup A
RSV B	respiratory syncytial virus subgroup B
RSVpreF	respiratory syncytial virus stabilized prefusion F subunit vaccine
[RSVpreF+BNT162b2]	Substudy A: combination RSVpreF and bivalent BNT162b2 (original/Omi BA.4/BA.5) vaccine

Abbreviation	Term
RT-PCR	reverse transcription–polymerase chain reaction
S1	spike protein S1 subunit
SADE	serious adverse device effect
SAE	serious adverse event
SAP	statistical analysis plan
SARS	severe acute respiratory syndrome
SARS-CoV	severe acute respiratory syndrome coronavirus
SARS-CoV-2	severe acute respiratory syndrome coronavirus 2
Screat	serum creatinine
Scys	serum cystatin C
SD	standard deviation
SIIIV	seasonal inactivated influenza vaccine
SmPC	summary of product characteristics (European Union)
SoA	schedule of activities
SOP	standard operating procedure
SRSD	single reference safety document
ST-T	ST-segment and T-wave
SUSAR	suspected unexpected serious adverse reaction
TBA	to be advised
T bili	total bilirubin
Th1	T-helper type 1
TOC	table of contents
UADE	unanticipated adverse device effect
UK	United Kingdom
ULN	upper limit of normal
US	United States
USADE	unanticipated serious adverse device effect
USPI	United States package insert
VE	vaccine efficacy
VRBPAC	Center for Biologics Evaluation and Research Vaccines and Related Biological Products Advisory Committee (United States)
WHO	World Health Organization
WOCBP	woman/women of childbearing potential
WT	wild type

